- To assess changes in vascular and SSc-PAH associated biomarkers following treatment with treprostinil at 1 year compared to baseline.
- To assess bone markers P1NP and C-telopeptide levels at baseline and at 1 year
- To assess baseline cortical area and cortical porosity measured by HR-pQCT in SSc patients with calcinosis.
- To assess osteoclastogenesis using PBMCs cultures at baseline and at 1-year

3. Hypothesis:

We hypothesize that calcinosis is a result of microvascular injury and ischemic damage, and that therefore treprostinil may be beneficial in the treatment of calcinosis in patients with SSc.

4. Study design:

This prospective open-label trial will enroll 12 patients with SSc and at least one calcinotic lesion of the hands that is palpable on physical examination and also measureable on hand radiographs. Each subject will undergo a screening evaluation 4 weeks before treatment with the study drug is initiated. Each subject will receive treprostinil 0.125 mg TID orally, which will be increased by 0.125 mg TID every 3 to 4 days as tolerated. Follow-up evaluations will be performed every 3 months over a 12-month period of time.

5. Study population:

The population for this study will consist of adult SSc patients with evidence of at least one calcinotic lesion of the hands that is palpable on physical examination and also measureable on hand radiographs.

Key inclusion criteria:

- Signed written informed consent
- Age > 18 years of age
- Diagnosis of limited or diffuse cutaneous systemic sclerosis (SSc) according to the revised 2013 ACR/EULAR classification criteria for SSc[7]
- Radiological and physical examination evidence of at least one subcutaneous calcium deposition in the hands that is clinically apparent as part of routine clinical care.
- If female of childbearing potential, the patient must have a negative pregnancy test at screening and baseline visits
- Oral corticosteroids (≤ 10 mg/day of prednisone or equivalent) and NSAIDs are permitted if the patient is on a stable dose regimen for ≥ 2 weeks prior to screening and throughout the study
- Calcium channel blockers, alpha-1-antagonists, ACE-inhibitors, angiotensin receptor blockers, and protein-pump inhibitors are permitted as long as the doses are stable for 4 weeks prior to screening and throughout the study
- Women of childbearing potential must agree to use adequate contraception when sexually active with any combination of at least 2 effective methods of birth control (except for women who have a partner who is sterile, i.e. due to vasectomy)

Key Exclusion Criteria:

- Rheumatic disease other than SSc
- Patients with pulmonary arterial hypertension (PAH), NYHA Class III or IV, as determined by right heart catheterization or on PAH approved medications for PAH
- Patients with moderate or severe hepatic impairment (Child Pugh Class C), or transaminase elevation (ALT or AST) > 3 x the upper limit of normal at screening visit
- Patients with diverticulosis
- Hemoglobin < 75% of the lower limit of the normal range
- Systolic blood pressure < 95 mmHg or diastolic blood pressure < 50 mmHg
- Patients who are hemodynamically unstable, or have acute renal, cardiac or pulmonary failure, or any life-threatening condition.
- Concurrent malignancy except non-melanoma skin cancers
- Patients receiving specific (sildenafil, tadalafil) or unspecific phosphodiesterase-5 inhibitors (dipyridamole, theophylline), endothelin receptor antagonists, prostanoids, riociguat, or NO donors (nitrates) within 4 weeks of screening
- Patients receiving bisphosphonates, warfarin, colchicine, minocycline, intravenous immunoglobulins, or biological agents including abatacept or rituximab within 4 weeks of screening
- Patients receiving local treatments for calcinosis of the hands including surgical removal or intralesional steroid injections within 12 weeks of screening or throughout the study.
- Patients who have participated in another clinical trial of an investigative agent within 30 days of screening (or 5 half-lives of the investigational drug, whichever is longer)
- Pregnant or nursing women
- Patients with a history of drug or alcohol abuse within 6 months of screening
- Any medical condition that, in the opinion of the investigator, might interfere with the subject's participation in the study or poses an added risk for the subject
- Inability to comply with study and follow-up procedures

6. Description of the treatment:

United Therapeutics will provide treprostinil labeled for investigational use. The Sponsor/Investigator of the trial will ensure maintenance of complete and accurate records of the receipt, dispensation, and disposal or return of all trial drug in accordance with Title 21 Code of Federal Regulations (C.F.R.), Part 312.57 and 312.62 and United Therapeutics requirements.

Treprostinil

Treprostinil (Orenitram®) is a prostacyclin vasodilator indicated for the treatment of pulmonary arterial hypertension (WHO Group 1) to improve exercise capacity. The chemical name of Orenitram® is Acetic acid, 2-[[(1R,2R,3aS,9aS)-2,3,3a,4,9,9a-hexahydro-2-hydroxy-1-[(3S)-3-hydroxyoctyl]-1H-benz[f]inden-5-yl]oxy]-, complexed with 2,2'-iminobis[ethanol] (1:1). The molecular formula is C₂₃H₃₄O₅C₄H₁₁NO₂, and its molecular weight is 495.65. Orenitram® is an extended release osmotic tablet for oral administration, and it is formulated as the diolamine salt of treprostinil, a tricyclic benzindene analogue of prostacyclin. It is available in the following four strengths: 0.125 mg (white tablet imprinted with UT 0.125), 0.25 mg (green tablet imprinted with UT 0.25), 1 mg (yellow tablet imprinted with UT 1), and 2.5 mg (pink tablet imprinted with UT 2.5). The formulations also contain xylitol, maltodextrin, sodium lauryl sulfate, magnesium

stearate, cellulose acetate, triethyl citrate, polyvinyl alcohol, titanium dioxide, polyethylene glycol, and talc. In addition tablets may contain colorants FD&C Blue #2, iron oxide yellow, and iron oxide red. The imprinting ink contains shellac glaze, ethanol, isopropyl alcohol USP, iron oxide black, n-butyl alcohol, propylene glycol, and ammonium hydroxide.

Mechanism of Action

The major pharmacologic actions of treprostinil are direct vasodilation of pulmonary and systemic arterial vascular beds, inhibition of platelet aggregation, and inhibition of smooth muscle cell proliferation.

Storage

Treprostinil must be stored at 25°C (77°F); excursions 15°C to 30°C (59°F to 86°F). For further details, see the Investigator Brochure and the Orenitram® Package Insert.[8]

Dosage and Administration

Initiate treprostinil at 0.125 mg TID (every 8 ± 2 h), with dose escalation of an additional 0.125 mg TID every 3 to 4 days as tolerated. No dose changes will be allowed for 5 days before the month 12 visit. [9] Give with food, swallow tablets whole, and use only intact tablets; do not crush, split, or chew. The maximum dose, dose escalation or titration will be done at the Investigator's discretion based upon individual subject tolerability. Patients with mild hepatic impairment (Child Pugh Class A) should initiate treprostinil at 0.125 mg TID, and increment at 0.125 mg TID every 6 to 8 days.[8]

Criteria for Treatment Discontinuation

Treatment will be discontinued in the following circumstances:

- Patients who wish to withdraw from further participation
- Patients with a serious or life-threatening adverse event that in the opinion of the investigator is directly attributable to the study drug
- The patient deviated from the protocol
- The patient's behavior is likely to undermine the validity of his / her results
- Patients who have a positive pregnancy test during the study
- Patients who develop any condition that in the opinion of the investigator could be worsened by further treatment with the study drug

Criteria for Stopping Rules

The study may be stopped at any time if, in the opinion of the Investigator and / or Sponsor, continuation of the study represents a serious medical risk to the subjects. This may include, but is not limited to, the presence of serious, life-threatening, or fatal adverse events or adverse events that are unacceptable in nature, severity, or frequency. The Sponsor reserves the right to discontinue the study for any reason at any time.

Down titration of study medication

Following the 12-month study assessments, patients will be titrated off study drug. Subjects discontinuing treprostinil, upon exiting the study at the End of Study visit or at early termination, who are receiving doses greater than 2 mg TID, should be tapered in 25% increments every 24 hours based on their End of Study dose prior to discontinuation. Once a dose of 2 mg TID or less is

reached, the subject can discontinue treprostinil. For example, a subject who reached an End of Study dose between 6 and 12 mg TID would decrease by 2 mg TID every 24 hours, and a subject who reached an End of Study dose between 2 and 6 mg TID would decrease by 1 mg TID every 24 hours.

7. Estimated duration: 14 months

8. Time and events schedule and description of assessments:

Assessments:

Screening Visit (1 month prior to treatment):

- Informed consent
- Review of inclusion and exclusion criteria
- Complete medical history including scleroderma diagnosis
- Review of concomitant medications
- Complete physical examination including examination of calcinosis, digital ulcers, vital signs, height/weight, and Modified Rodnan skin score (MRSS)
- Electrocardiogram (EKG)
- Laboratory tests: CBC with differential, comprehensive metabolic panel, and urinalysis
- Urine pregnancy test (females of child bearing potential only)
- Review of adverse events

Baseline Visit (0 month):

- Review of concomitant medications
- Complete physical examination with vital signs, and MRSS
- Examination of calcinosis and digital ulcers
- Laboratory tests: CBC with differential, comprehensive metabolic panel, and urinalysis
- Urine pregnancy test (females of child bearing potential only)
- Questionnaires: SHAQ, Cochin hand functional scale, SF-36 assessment of health status, Mawdsley Calcinosis Questionnaire, Physician/Patient Global Assessment of calcinosis severity, and Raynaud's Condition Score.
- Review of adverse events
- Study drug dispense/return
- Radiological assessment of calcinosis
- Skin biopsy
- Blood for biomarker analyses
- SPY assessment of superficial blood flow
- Anthropometric measurements
- High resolution peripheral quantitative computed tomography (HRpQCT)
- Handgrip strength measurement

At 3 months visit:

- Review of concomitant medications
- Examination of calcinosis and digital ulcers
- Urine pregnancy test (females of child bearing potential only)
- Questionnaires: SHAQ, Cochin hand functional scale, SF-36 assessment of health status, Mawdsley Calcinosis Questionnaire, Physician/Patient Global Assessment of calcinosis severity, and Raynaud's Condition Score.

- Blood for biomarker analyses
- Review of adverse events
- Study drug dispense/return

At 6 months visit:

- Review of concomitant medications
- Examination of calcinosis and digital ulcers
- Complete physical examination with vital signs, and MRSS
- Laboratory tests: CBC with differential, comprehensive metabolic panel, and urinalysis
- Urine pregnancy test (females of child bearing potential only)
- Questionnaires: SHAQ, Cochin hand functional scale, SF-36 assessment of health status, Mawdsley Calcinosis Questionnaire, Physician/Patient Global Assessment of calcinosis severity, and Raynaud's Condition Score.
- Review of adverse events
- Study drug dispense/return

At 9 months visit:

- Review of concomitant medications
- Examination of calcinosis and digital ulcers
- Urine pregnancy test (females of child bearing potential only)
- Questionnaires: SHAQ, Cochin hand functional scale, SF-36 assessment of health status, Mawdsley Calcinosis Questionnaire, Physician/Patient Global Assessment of calcinosis severity, and Raynaud's Condition Score.
- Review of adverse events
- Study drug dispense/return

At 12 months visit:

- Review of concomitant medications
- Examination of calcinosis and digital ulcers
- Urine pregnancy test (females of child bearing potential only)
- Questionnaires: SHAQ, Cochin hand functional scale, SF-36 assessment of health status, Mawdsley Calcinosis Questionnaire, Physician/Patient Global Assessment of calcinosis severity, and Raynaud's Condition Score.
- Review of adverse events
- Study drug dispense/return
- Complete physical examination with vital signs, and MRSS
- Laboratory tests: CBC with differential, comprehensive metabolic panel, and urinalysis
- Radiological assessment of calcinosis
- Skin biopsy
- Blood for biomarker analyses
- SPY assessment of superficial blood flow
- EKG
- High resolution peripheral quantitative computed tomography (HRpQCT)

At 13-months visit:

- Review of concomitant medications
- Examination of calcinosis and digital ulcers

- Review of adverse events
- Study drug returnComplete physical examination with vital signs

Study Flowchart:

Study Flowchart: Study phase	Pre- treatment phase	Treatment phase			Follow-up phase		
Visit	Screening	Baseline	1	2	3	End	Follow-up
Month	-1	0	3	6	9	12	13
Informed consent	X						
Inclusion/exclusion criteria	X						
Medical history including SSc	X						
Concomitant medications	X	X	X	X	X	X	X
Physical examination	X	X		X		X	X
Examination of calcinosis and digital ulcers	X	X	X	X	X	X	X
Vital signs	X	X		X		X	X
Height/Weight	X						
EKG	X					X	
Laboratory tests*	X	X		X		X	
Urine pregnancy test	X	X	X	X	X	X	
Radiological assessment of calcinosis		X				X	
Scleroderma Health Assessment Questionnaire (SHAQ)		X	X	X	X	X	
Cochin Hand Functional Scale		X	X	X	X	X	
Mawdsley Calcinosis Questionnaire		X	X	X	X	X	
SF-36 assessment of health status		X	X	X	X	X	
Raynaud's Condition Score		X	X	X	X	X	
Physician/patient global assessment of calcinosis severity		X	X	X	X	X	
MRSS	X	X		X		X	
Skin biopsies		X				X	
Blood for biomarker analyses		X	X			X	
PBMC		X				X	
P1NP and C-telopeptide		X				X	
SPY		X				X	
XtremeCT II scans		X				X	
Adverse events	X	X	X	X	X	X	X
Study drug dispense/return *CRC_CMP_LIA		X	X	X	X	X	X

^{*}CBC, CMP, UA

Description of assessments:

Medical history including SSc: Significant past or present illnesses, current prescription or nonprescription medications (including vitamins and herbal products), and history of allergies or idiosyncratic responses to drugs should be noted.

Physical examination: A complete physical examination will be conducted by a physician at Screening, 6 months, and at end of study. Any significant changes to the subject's medical condition, physical examination, and concomitant medications should be documented throughout the course of the study. Any untoward medical experience should be recorded as an adverse event.

Examination of calcinosis and digital ulcers: Investigator will perform a thorough clinical examination looking for calcinotic deposits at each visit. We will use case report forms with picture images of the hands to record calcinosis and digital ulcers at each evaluation (Appendix A). We will define digital ulcer as an area with visually discernable depth and a loss of continuity of epithelial coverage in the volar aspect of the finger and distal from the proximal interphalangeal joints, which could be denuded (active) or covered by a scab or necrotic tissue (indeterminate). At each visit, the status of each digital ulcer will be rated as "A," a current active digital ulcer, "H", a completely healed ulcer, or "I," an ulcer with indeterminate status, as previously defined.[10]

Vital Signs: Systolic and diastolic blood pressure, heart rate, respiratory rate, and temperature (°C) will be measured prior to assessments and after sitting for 5 minutes at screening, baseline, 6 months, and 12 months. Vital signs should also be assessed in the case of abnormal clinical signs and symptoms.

Electrocardiogram (ECG): Twelve-lead ECGs will be recorded after at least 5 minutes rest in the semi-recumbent position at screening and at the end of the study at 12 months. Recordings should include lead II as a rhythm strip and contain at least 5 QRS complexes. ECG parameters collected (after at least 5 minutes rest) include heart rate, and PR interval, QT interval, QRS duration and any clinically significant abnormalities.

Laboratory tests: Blood and urine samples for the measurement and evaluation of CBC, CMP, and urinalysis (UA) will be collected at screening, 6 months and at the end of the study, and analyzed at Stanford laboratory.

Urine pregnancy test: urine beta-HCG will be measured in all female in reproductive age at all visits.

Radiological examination of calcinosis: Patients will have plain radiographs of the hands at baseline and at 1 year. [name] and [name] will serve as the blinded X-ray assessors.

Scleroderma Health Assessment Questionnaire (SHAQ): The SHAQ is a patient self-administered instrument, which has been previously validated in SSc and demonstrates meaningful clinical changes in the course of the disease over time. It is comprised of the HAQ-DI, a self-administered 20-question instrument that assesses a patient's level of functional ability and five scleroderma visual analogue scale (VAS) measurements to evaluate symptoms specific to SSc (Appendix B). [11-13]

Cochin Hand Function Scale (CHFS): CHFS is a questionnaire derived from 18 validated questions to assess functional disability and handicap due to hand involvement in rheumatoid arthritis. Each answer is scored on a scale of 0 (no difficulty) to 5 (impossible to do), with a maximum score of 90. A higher score indicates worse disability or handicap. The CHFS has been demonstrated as a reliable and valid assessment of hand function at the activity level in persons with SSc (Appendix C).[14, 15]

Mawdsley Calcinosis Questionnaire: The content of this questionnaire is patient-generated and includes 17 questions related to the impact of calcinosis rated from 0 (no limitation) to 10 (worst limitation possible) (Appendix D).

The Medical Outcomes Study 36-Item Short Form Health Survey (SF-36): The SF-36 is one of the most widely used instruments to assess quality of life in patients with systemic illnesses. It is a self-administered questionnaire covering eight areas: physical function, physical role, bodily pain, general health, vitality, social function, emotional role, and mental health. For each area, the score ranges from 0 (poorer health status) to 100 (better health status) (Appendix E). [16-24]

Patient and Physician global assessments: Patients and physicians will each independently rate the severity of calcinosis on a 10 cm VAS. The term "severity" will be used to measure the extent of disease activity and associated disability or discomfort the patient experiences during the indicated time period (Appendix F).[25]

Raynaud's Condition Score (RCS): We will measure changes in Raynaud's phenomenon (RP) by using the RCS, a self-assessment of RP activity using a 0–10 ordinal scale. The RCS incorporates the cumulative daily frequency, duration, severity, and impact of RP attacks (Appendix G).[25]

Modified Rodnan Skin Score (mRSS): The mRSS measures skin tightness and is the sum of scores from 17 surface anatomic areas (fingers, hands, forearms, arms, feet, legs, and thighs bilaterally, and face, chest, and abdomen singly) rated on a 0–3 scale (0=normal skin; 1=mild thickness; 2=moderate thickness; 3=severe thickness with inability to pinch the skin into a fold). The skin score will be the sum of the individual skin assessment scores and ranges from 0 (best possible outcome) to 51 (worst possible outcome) (Appendix H). [26-28]

Skin biopsies: We will collect two side-by-side skin samples to assess for vascular changes on histopathology and gene expression changes following treatment with treprostinil: one at baseline and one at the end of the study. This part of the study will be optional for participating patients. Skin biopsies will be obtained from a standard site on the forearm (extensor surface of forearm approximately 10 cm proximal to the olecranon, which is chosen for its uniform

involvement in patients with SSc). Two adjacent 5 mm punch biopsies (taken full thickness to subcutaneous fat) will be harvested from the site. This involves selecting an area to biopsy and wiping the skin with alcohol. Next, 1-2 cc of lidocaine with 1:100,000 epinephrine is introduced into the skin using a 30G needle. Two punch biopsies will then be taken and processed as described in appendix I. Next, the wound will be sutured with 1-2 4.0 nylon sutures. Wounds will be dressed with polysporin and a bandage. Verbal wound care instructions will be given. The first biopsy will be bisected: one half will be flash frozen in liquid nitrogen and half will be embedded in paraffin. The second biopsy will also be bisected: one half will be placed in RNA later, and the other half will be placed in a cryo-tube. (See appendix I for details)

Research blood: We will collect serum and peripheral blood samples to assess changes in vascular and SSc-associated biomarkers following treatment with treprostinil. Blood samples for the assessment of biomarkers will be drawn at baseline, 3 months, and end of study visit. Please see appendix for a complete list of biomarkers (Appendix J).

P1NP and C-telopeptide: Procollagen Type I Intact N Terminal Propeptide (P1NP), a marker of bone formation, and C-telopeptide, a marker of bone resorption, will be measured at baseline and 12 months to provide information about the rate of bone turnover, and to determine whether patients with calcinosis have high turnover rates.

PBMCs: PBMCs will be obtained for each participant at baseline to assess for abnormal osteoclastogenesis. A recent publication investigated whether acro-osteolysis (bone resorption of distal phalanges), a clinical feature often associated with digital ulcers and calcinosis[3], was associated with abnormal osteoclastogenesis in SSc patients. The authors found that hypoxia may enhance the formation of osteoclasts particularly in SSc patients with acro-osteolysis. We hypothesize that SSc patients with calcinosis will similarly demonstrate increased osteoclastogenesis, resulting in enhanced propensity to osteoporosis/bone loss. [29] We will obtain PBMCs at baseline and 12 months.

SPY: The SPY Near-Infrared Perfusion Assessment System (distributed by LifeCell Corp., Branchburg, N.J.; manufactured by Novadaq Technologies Inc., Richmond, BC, Canada) is an imaging technology that utilizes indocyanine green (ICG), and allows real-time visual assessment of superficial blood flow.[30]

XtremeCT II scan: The latest-generation high-resolution peripheral quantitative computed tomography (HR-pQCT) XtremeCT II scan is a novel technology with dramatically improved spatial resolution. It is able to define the cortical and trabecular surfaces of the bones in a three-dimensional fashion, and therefore provides information on bone microarchitecture as well as bone density. The XtremeCT II machine at Stanford University is one of 10 in the United States. We will perform HR-pQCT at baseline and at 12 months to assess for changes in cortical area and cortical porosity.

Safety: During the study, the primary assessment of safety will be changes in vital signs, clinical laboratory parameters, EKG, and the development of adverse events.

9. Safety monitoring and reporting

Definitions:

Adverse Event (AE): An AE is any untoward medical experience occurring to a subject during a clinical trial whether or not it is related to the study drug. An AE may include an intercurrent illness, injury, or any other concomitant impairment of the subject's health, as well as abnormal laboratory findings if deemed to have clinical significance. AEs may also include worsening of an existing symptom or condition or post-treatment events that occur as a result of protocol-mandated procedures.

Severe Adverse Event (SAE): A SAE is an AE occurring at any dose that results in any of the following outcomes:

- Death
- A life-threatening AE
- Inpatient hospitalization or prolongation of existing hospitalization
- A persistent or significant disability / incapacity
- A congenital anomaly / birth defect

In addition, important medical events that may not result in death, be life-threatening, or require hospitalization may be considered serious when, based upon appropriate medical judgment, they may jeopardize the subject and require medical / surgical intervention to prevent one of the outcomes listed above. Examples of such medical events include allergic bronchospasm requiring intensive treatment in an emergency room or at home, blood dyscrasias or convulsions that do not result in hospitalization, or the development of drug dependency or drug abuse. Life threatening means that the subject was, in the view of the Investigator, at immediate risk of death from the event as it occurred. It does not mean that the event, had it occurred in a more severe form, might have caused death.

Reporting Responsibilities:

In the event of an adverse event, the first concern will be for the safety of the patients. Investigators are required to collect and document all adverse events (AEs) and non-related serious adverse events (SAEs). All SAEs, regardless of expectedness or causality, must be reported to the Sponsor by fax (+ 1 [contact] or other appropriate number) within 24 hours of awareness. A completed SAE report form along with any relevant hospital records and autopsy reports should be faxed to the Drug Safety Department at United Therapeutics Corporation. A follow-up SAE report form must be forwarded to the Drug Safety Department at United Therapeutics Corporation within 48 hours of the receipt of any new / updated information. The Investigator must also promptly notify their Investigational Review Board (IRB) or Ethics Committee (EC) of the SAE, including any follow-up information, in accordance with applicable national regulations and guidelines set forth by the IRB or EC. All documents related to AEs (serious, non serious, related, or not) will be readily available for review, should the need arise.

An AE or SAE occurring during the study must be documented in the subject's source documents and on the appropriate CRF page. Information relating to the AE such as onset and cessation date and times, intensity, seriousness, relationship to study drug, and outcome is also to be documented in the CRF. Where possible, AEs should be recorded using standard medical terminology. If several signs or symptoms are clearly related to a medically defined diagnosis or

syndrome, the diagnosis or syndrome should be recorded on the CRF page, not the individual signs and symptoms.

All AEs should be followed until either resolution (or return to normal or baseline values), until they are judged by the Investigator to no longer be clinically significant, or for at least 4 weeks if the AE extends beyond the final visit. All SAEs that occur during the study will be followed until resolution, death, or the subject is lost to follow-up even if they are ongoing more than 4 weeks after completion of the final visit. Supplemental measurements and / or evaluations may be necessary to investigate fully the nature and / or causality of an AE or SAE. This may include additional laboratory tests, diagnostic procedures, or consultation with other healthcare professionals. CRF pages should be updated.

10. Statistical Considerations

[figure not shown]
Statistical analysis:

Descriptive statistics and frequency distributions of all variables of interest will be reported as proportions (%) for categorical variables and as mean ± standard deviation or median (range) for continuous variables. Baseline to 12-month differences and 95% confidence intervals will be calculated for scored outcomes (x-ray score, MRSS, physician's global assessment by VAS, and quality of life measurements). For the primary efficacy endpoint, mean change and standard deviation in calcinosis burden assessed by radiograph from baseline to 12-month visit, we will use Student's t-test. The mean rate of change of calcinosis in radiograph will be calculated with the following formula: (Year 1 XR score – Baseline XR score)/time. XR score is defined as: sum of scores for 22 weighted areas affecting each hand: %area coverage (0-100) X density (1-3) X weight for each area.[6]

Sample size calculation:

We will need 9 paired radiographs (9 patients) at 1-year to provide >80% power to detect a mean change in x-ray score of 12.0 (equivalent to a minimally significant change in score of 25%) with a SD of 8.2 with moderate correlation r=0.5 using a two-sided test at alpha 0.05 level. We estimate a 15% dropout rate based on prior clinical trials. Hence, the total number of subjects needed to obtain 9/0.85 subjects who complete the study is 11 subjects. Also, due to the small sample size, we plan to use Wilcoxon signed rank test to analyze the effects. Thus, we anticipate losing about 10% of power due to using a non-parametric test. As a result, the sample size is further adjusted to 11/0.9 = 12. Statistical significance will be defined as $p \le 0.05$.

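### The hepatic exclusion names two grades of impairment but cites only Child Pugh Class C; the parenthesis should read Class B or C

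*Combined protocol and SAP*

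**What the plan says.** Section 5, Key Exclusion Criteria, excludes "Patients with moderate or severe hepatic impairment (Child Pugh Class C", with the parenthesis closing straight after the class. The same bullet has a second, separate limb: "or transaminase elevation (ALT or AST) > 3 x the upper limit of normal at screening visit". A later bullet lets the investigator exclude a patient with any medical condition that "poses an added risk for the subject".

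Section 6, Dosage and Administration, sets the general schedule, starting at 0.125 mg TID "with dose escalation of an additional 0.125 mg TID every 3 to 4 days as tolerated". It then gives one hepatic rule. On the starting dose it says: "Patients with mild hepatic impairment (Child Pugh Class A) should initiate treprostinil at 0.125 mg TID". For later steps in that group the interval is longer: "increment at 0.125 mg TID every 6 to 8 days". The ceiling and pace are otherwise a matter for the investigator, by "discretion based upon individual subject tolerability".

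Neither section mentions Child Pugh Class B, and no other part of the document does.

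**The concern.** An eligibility criterion should give the same answer whoever applies it. This one can give two. By its words, a moderately impaired patient is out. By its class, only Class C is out, and a patient between A and C is in.

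The criterion protects safety. The protocol itself treats even mild impairment as a reason to escalate more slowly. A more impaired patient admitted by class would meet no hepatic rule in this protocol and would fall to the general schedule, which has the shorter interval between steps. Safety and tolerability is a primary endpoint in a trial of 12 patients. Under the section 8 flowchart, the next scheduled visit after baseline is at month 3, and the next scheduled vital signs and laboratory tests are at month 6.

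**Working it through.** There is no figure in the plan to reproduce. The check sets the two hepatic statements side by side.

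| Grade in words | Child Pugh class given | Eligibility | Hepatic titration rule |
|---|---|---|---|
| Mild | A (section 6) | Enrolled, since a dosing rule is given | Steps every 6 to 8 days |
| Moderate | None given | Excluded by the words of section 5; not excluded by the class cited | None |
| Severe | C (section 5) | Excluded by words and by class | None needed |

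1. Section 6 fixes one end of the scale: mild is Class A.
2. Section 5 uses the two grades above mild and cites one class, C.
3. There are two ways to attach the parenthesis. If it defines both grades, the class between A and C is left out, although moderate impairment is named. If it defines only the severe grade, the moderate grade has no class. The annotation is incomplete either way.
4. The classes run in order from A to C. With mild as A and severe as C, moderate falls on B. This step is an inference; the documents do not state it.
5. Test the possible meanings against section 6. If B and C are excluded, every enrolled hepatic patient is Class A and has a titration rule, so the sections agree. If only C is excluded, Class B patients are enrolled with no hepatic rule, and the word moderate does no work.
6. Only the first meaning leaves no gap between the sections.

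The transaminase limb does not settle the matter. It is an alternative ground for exclusion and defines no Child Pugh class.

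**The case against.** The strongest reply is that the words already exclude the patient in question. The parenthesis follows the word for severe disease and can be read as a gloss on that alone, which makes this a missing label and not a contradiction. Section 6 points the same way. Harm then needs a reader who disregards a word in the criterion and does not invoke the added-risk exclusion. Titration is also as tolerated and at the investigator's discretion. With 12 patients and a combined Sponsor/Investigator, those applying the criterion are probably close to those who wrote it.

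Much of this stands. The intended meaning can be recovered, and the safeguards lower the risk. They do not correct the text, however: each relies on individual judgement, and recovering the meaning requires comparing two sections and supplying a class that neither names.

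The absence of a titration rule for moderate impairment is established only for this protocol. The hepatic rule cites the package insert, and section 6 (Storage) refers to that insert and the Investigator Brochure for further details. Neither was available here.

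A reader might also infer a size of harm from the two schedules. The intervals alone give escalation-rate ratios from 6/4 = 1.5 to 8/3 = 2.67. The arithmetic is right, but it does not measure excess risk. It presumes a mis-enrolled patient who takes every permitted step, and it uses the Class A schedule as the benchmark for moderate impairment, which the documents do not do.

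**Conclusion.** The point holds as a wording error in an operative safety exclusion: the criterion can give two answers for a moderately impaired patient. The mismatch itself is plain on the page. The consequence is conditional on someone screening by the cited class, and its size cannot be estimated, because the documents give neither the frequency of moderate impairment nor a reference schedule for it. Identifying moderate with Class B rests on the ordering of the classes.

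A reader might infer that deleting the word moderate would be an equally good repair. The documents do not support that. It would admit patients whom the present words exclude, and any titration rule written for them would have no basis in the protocol.

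Nor does the error show that the sponsor meant to enrol moderate impairment; the mild-only dosing rule suggests the opposite. Sample size, power and analysis do not change. The correction should be made because it removes a gap in patient protection at almost no cost.

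**What to change.** In section 5, Key Exclusion Criteria, change the parenthesis in the hepatic exclusion to (Child Pugh Class B or C). Leave the words of the criterion, the transaminase limb and the Class A titration rule in section 6 as they are. The cost is a one-line protocol correction.
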